2 INTRODUCTION

2.1 STUDY RATIONALE

Vulnerability to the deleterious mood effects of normal changes in reproductive hormones is a likely underpinning to reproductive mood disorders. The menopause transition (MT) is associated with pronounced hormonal variability (within the context of relative E2 deprivation) and substantially increased risk for clinically impairing anxiety and anhedonia. Anxiety is characterized by cognitive bias to

interpret ambiguous stimuli in a threat-related manner. Anhedonia can be defined by decreased motivation to approach rewards. The neurobiologically-based constructs of 'threat reactivity' and 'approach motivation' provide a framework for studying the pathophysiology of the clinical impairment experienced by 25% of women in the MT. Although the causes of affective symptoms in the MT remain unknown, severe life stress proximate to the MT is a strong predictor. Framed within a diathesis-stress model, the primary objective of this research is to determine the pathophysiological mechanisms of estradiol (E2) in the clinical anxiety and anhedonia seen in the MT. Specifically whether E2 variability or E2 levels predict exaggerated hypothalamic-pituitary-adrenal (HPA) axis reactivity and impaired recovery to stress and, in turn, deficits in behavioral indices of threat responsivity and approach motivation and symptoms of anxiety and anhedonia. The secondary objective of the research is to use a hormonal manipulation as a mechanistic probe to stabilize E2 variability in premenopausal ranges and determine if HPA axis reactivity/recovery represents a biomarker of behavioral and symptom responses to E2 stabilization.

A total of 250 women in the early or late MT who are eligible for the hormonal probe will be recruited to reflect the full continuum of anxiety and anhedonia symptoms based on self-report to the State-Trait Anxiety Inventory and the Snaith-Hamilton Pleasure Scale, respectively. At baseline week 8, HPA axis (plasma cortisol) response to the Trier Social Stress Test and behavioral measures of threat responsivity (via Dot-Probe task) and approach motivation (Effort Expenditure for Rewards Task 'EEfRT') will be determined. Using transdermal E2 as a pharmacological probe to stabilize variability of E2 in premenopausal ranges, women will then be randomized to transdermal E2 (0.10 mg) or placebo for 16 weeks. This is not a clinical efficacy trial. We will use an RCT design with a hormonal manipulation to investigate the pathophysiologic role of E2 variability (or E2 levels) in HPA axis dysregulation and, in turn, threat responsivity and approach motivation. HPA axis reactivity to stress and behavioral responses to the Dot-Probe and EEfRT tasks, as well as self-report symptoms on the STAI and SHAPS measures will be assessed at weeks 8, 12, and 16 during the 16-week probe.

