1 PROTOCOL SUMMARY

1.1 SYNOPSIS

Title:	The Menopause Transition: Estrogen Variability, HPA axis and Affective Symptoms
Study Description:	Women in the menopause transition ('perimenopause') are exposed to extreme hormone variability, tend to experience a unique set of severe stressors (e.g., divorce, death of loved ones), and are also at substantially elevated risk to suffer from mood and anxiety disorders. The purpose of this research is to understand the mechanisms by which variability in estradiol (E2) is associated with the symptoms of anxiety and anhedonia (loss of interest and pleasure - a common symptom of depression). By stabilizing E2 variability with a hormonal manipulation, this research will determine the degree to which the E2 variability (or E2 levels) plays a causal role in perimenopausal anxiety and anhedonia symptoms and whether it does so by affecting biological responses to stress.
Objectives:	
Primary Objectives:
 
1. Change over time in anxiety score from State-Trait Anxiety Inventory [Time Frame: Baseline (Week 8), Weeks 16, 20 and 24]2. Change over time in anhedonia score from the Snaith-Hamilton Pleasure Scale [Time Frame: Baseline (Week 8), Weeks 16, 20 and 24] 
Secondary Objectives:
 
1. Change over time in AUC cortisol stress response [Time Frame: Baseline (Week 8), Weeks 16, 20 and 24]2. Change over time in threat reactivity from Dot Probe behavioral task [Time Frame: Baseline (Week 8), Weeks 16, 20 and 24]

3. Change over time in measure of effort for motivation and anhedonia from Effort Expenditure for Reward Task [Time Frame: Baseline (Week 8), Weeks 16, 20 and 24]

Endpoints:

Primary Endpoints:

1. Change in STAI score [Time Frame: Baseline (Week 8), Weeks 16, 20 and 24]
2. Change in SHAPS score [Time Frame: Baseline (Week 8), Weeks 16, 20 and 24]

Secondary Endpoints:

1. Change in AUC cortisol response [Time Frame: Baseline (Week 8), Weeks 16, 20 and 24]
2. Change in “threat bias” score from Dot Probe task [Time Frame: Baseline (Week 8), Weeks 16, 20 and 24]
3. Change in “hard choice” score from EEfRT [Time Frame: Baseline (Week 8), Weeks 16, 20 and 24]

Study Population:

250 medically healthy female volunteers aged 45-60 undergoing natural menopause transition who meet STRAW+10 criteria for early or late menopause transition and are candidates for transdermal E2 and have had a normal mammogram in the previous 12 months.

Phase:

N/A

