Description of Sites/Facilities Enrolling Participants:

Subjects are recruited from the area surrounding Chapel Hill, North Carolina and will be enrolled at the UNC-CH laboratory site located at [name]. Medical screening, including the gynecological exam and screening mammogram will occur at the UNC Medical Center on the UNC-CH campus. This study is not intended to include sites outside of the United States.

Description of Study Intervention:

Subjects randomized to the active treatment arm will wear a transdermal estradiol patch (0.1mg) every day for 16 weeks, changing the patch every 7 days. They will also take 200mg of micronized progesterone oral capsules every day for 12 days 8 weeks after randomization to estradiol and again at the end of the 16th week of randomization to estradiol. Subjects randomized to the placebo arm will follow the same regimen using matching placebo transdermal patches and placebo capsules.

Study Duration:

Enrollment will occur for approximately 54 months and data analysis will occur for 6 months following the close of enrollment. Estimated total study duration is 60 months.

Participant Duration:

Following medical screening, individual participation study duration is 6 months (24 weeks). Randomization to active/placebo treatment arm occurs at week 8, and subjects will be in the intervention phase for a total duration of 16 weeks.

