4.2 SCIENTIFIC RATIONALE FOR STUDY DESIGN

THIS IS NOT A CLINICAL EFFICACY TRIAL. However, we will employ an RCT design to study the pathophysiologic role of E2 variability [or levels] in the clinical symptoms of women in the MT. Under double-blind procedures, subjects will be randomized to receive 17 β - E2 or placebo for 16 weeks. The study biostatistician will create the randomization scheme and UNC Investigational Drug Services will manage the randomization and dispensing of hormones in blinded form. For those randomized to transdermal E2 (n=60), each will wear a patch (generic for Climara[®]) delivering 0.10 mg E2/24 hours. Those randomized to placebo (n=60), will wear a patch identical in appearance (3M Pharmaceuticals).

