6.3 MEASURES TO MINIMIZE BIAS: RANDOMIZATION AND BLINDING

Under double-blind procedures, subjects will be randomized to receive E2 or placebo for 16 weeks. The study biostatistician will create the randomization scheme and UNC Investigational Drug Services will manage the randomization and dispensing of hormones in blinded form. For those randomized to transdermal E2 (n=60), each will wear a patch delivering 0.10 mg E2/24. Those randomized to placebo (n=60), will wear a patch similar in appearance.

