9.2 SAMPLE SIZE DETERMINATION

Sample size calculations were performed for the primary outcome measures. Correlation and effect size estimations were based on previously published literature ^{173,174}. With a sample size of N=120 and performing hypothesis tests at two-sided alpha=.05 and a correlation of >.25 among repeated measures, we have >90% power to detect a small effect size of .15.

The G*power software was used to determine the sample size ¹⁷⁵, based on a repeated measures ANOVA with within-between interaction ^{173,174}. We conservatively account for 15% (n =18) withdrawal following randomization, yielding 138 women who complete the protocol (powered for 120). This sample size will provide sufficient power to address secondary endpoints. No exploratory analyses will be performed.

By using proc mixed (not GLM), we will apply an analysis which is relatively robust to missing data. Before applying proc mixed, we will check for the randomness of missing data.

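### Three sample sizes (250 recruited, 120 randomised, 138 in Section 9.2) are never reconciled, and 15% withdrawal from the printed 60 per arm leaves 102 completers with about 84% power

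*Combined protocol and SAP*

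**What the plan says.** The protocol gives a count of participants in five places.

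- **Section 1.1 (Study Population):** "250 medically healthy female volunteers aged 45-60 undergoing natural menopause transition who meet STRAW+10 criteria for early or late menopause transition". The same entry requires that they be candidates for transdermal estradiol and have a recent normal mammogram.
- **Section 2.1:** "A total of 250 women in the early or late MT who are eligible for the hormonal probe will be recruited". After the week 8 baseline tests, "women will then be randomized to transdermal E2 (0.10 mg) or placebo for 16 weeks". That sentence gives no number.
- **Section 4.2:** 60 women randomised to estradiol and 60 to placebo.
- **Section 6.3:** the same split, with "For those randomized to transdermal E2 (n=60), each will wear a patch" for the active arm and 60 for placebo.
- **Section 9.2:** more than 90% power at N = 120. Then "We conservatively account for 15% (n =18) withdrawal following randomization", which brings the total to 138. The text calls these 138 the women who complete, while noting that the power is for 120.

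On timing, the schema puts screening and enrolment at week 0, and the synopsis says "Randomization to active/placebo treatment arm occurs at week 8". Section 9.3 defines the analysis set as everyone randomised. Section 9 says that there is no separate SAP, so no other document is available to settle the number.

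**The concern.** The size of the randomised population is not fixed. The analysis set in Section 9.3 is everyone randomised, and the power claim in Section 9.2 depends on how many of those women provide data. A final randomised count of 120 could be called as planned under Sections 4.2 and 6.3, and 138 could be called as planned under Section 9.2. The text in Sections 1.1 and 2.1 does not clearly exclude a larger number. The DSMB, which reviews enrolment every six months, has no single number at which randomisation closes.

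There are two separate gaps. The first is between the 250 recruited and the number randomised: no loss rate is given for the eight weeks before randomisation. The second, which matters more for power, is between the 120 in the randomisation sections and the 138 in the sizing section. If randomisation stops at 120, the allowance for withdrawal has not been made.

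**Working it through.** **Inputs.** From Section 9.2: N = 120, two-sided alpha .05, correlation above .25 (taken at .25), effect size .15 (read as Cohen's f), and a repeated-measures ANOVA within-between interaction. From Section 9.1: m = 4 visits (weeks 8, 16, 20, 24). From Section 4.1: k = 2 arms. Sphericity is assumed, because the protocol gives no correction value.

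**Formula.** Noncentral F with λ = f² × N × m / (1 − r), df1 = (k − 1)(m − 1) = 3, df2 = (N − k)(m − 1).

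**Step 1: reproduce the plan's power.** At N = 120, λ = 0.0225 × 120 × 4 / 0.75 = 14.4 and df2 = 118 × 3 = 354. Power is 90.2%, and 120 is the smallest even N that reaches 90%. The stated power reproduces.

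**Step 2: reproduce the 138.** 15% of 120 is 18, and 120 + 18 = 138. The figure reproduces as 120 × 1.15. Inflating so that 120 remain after 15% loss gives 120 / 0.85 = 141.2, that is 142.

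**Step 3: check the label on 138.** Losses are added to completers to get the number randomised, so 138 can only be a number to randomise. After 15% withdrawal, 138 × 0.85 = 117.3, about 117 completers. The 18 women are 18/138 = 13.0% of 138, not 15%.

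**Step 4: the gap from 250.**

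- 250 to 138: (250 − 138)/250 = 44.8%
- 250 to 120: (250 − 120)/250 = 52.0%

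The protocol states no pre-randomisation loss rate to compare with these.

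**Step 5: completer-based power under each reading, with 15% withdrawal.**

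| Randomised | Completers | λ | df2 | Power |
|---|---|---|---|---|
| 120 (60 per arm) | 120 × 0.85 = 102 | 12.24 | 300 | 84.3% |
| 138 (69 per arm) | about 117 | 14.04 | 345 | 89.3% |
| 250 | about 212 | 25.44 | 630 | 99.4% |

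With no withdrawal at all, power is 90.2% at 120, 94.0% at 138 and 99.8% at 250.

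**Step 6: sensitivity to the correlation.** The plan says above .25. At r = .5 with 102 completers, λ = 0.0225 × 102 × 4 / 0.5 = 18.36 and power is 96.0%. The shortfall in the first row therefore applies at the lower end of the plan's correlation range.

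**The case against.** The strongest reply is that 250 and 120 count different things: 250 women enter a baseline phase at week 0, and a subset is randomised at week 8. There is textual support for this. Section 2.1 makes the association of estradiol variability or levels with outcomes the primary objective, and the hormonal manipulation the secondary one. There are also several routes out before randomisation: screen failure (5.4), the pregnancy test at the baseline session (5.1 and 8.3.9), migraine with aura before randomisation (7.2), and withdrawal for excluded medication or non-compliance (7.2), which is not limited to the period after randomisation. This stands as a possible reading. Against it, the 250 are described as already eligible for the hormone, no rate is attached to any of these routes, and no section says that only a subset is randomised.

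Three stronger readings are tempting, and the documents do not support them.

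- A reader might infer that the 15% allowance fails because it does not lead to 250. The plan defines it as withdrawal after randomisation and uses it only to go from 120 to 138, which it does.
- A reader might infer that 125 women will receive active hormone and that the analysis set is 250. Neither figure is printed. The randomisation statement in Section 2.1 carries no number, the synopsis attaches no randomised number to its 250, and both sections that do give one (4.2 and 6.3) say 60 per arm.
- A reader might infer that the risk section depends on the disputed count. Section 2.3 works from percentages, rates and hazard ratios and uses no count derived from 250.

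It is also fair to say that the analysis in Section 9.4 is a mixed model on everyone randomised. Women who withdraw after week 16 or 20 still contribute, so completer-based power understates the real figure.

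**Conclusion.** The point holds as an inconsistency between sections, not as a failed calculation: both the power at 120 and the 138 reproduce. What is missing is a link between 250, 120 and 138, and a correct label for 138.

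The practical size is this. If the 60 per arm in Sections 4.2 and 6.3 are what is randomised, 15% withdrawal leaves 102 completers and power of about 84%, against the claim of more than 90%. If 138 are randomised, about 117 complete and power is about 89%, only just short of the claim. The 250 poses no threat to power under any reading. Its problem is that it leaves the number randomised open and implies an unstated loss of 44.8% or 52.0%.

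These figures assume f = .15, a correlation of exactly .25, four visits, sphericity, and completers only. A higher correlation or credit for partial data would raise them, and departure from sphericity would lower them (at N = 120, an epsilon of .75 gives 82.8%). The number randomised should be settled in the text, because the analysis set and the power claim both rest on it.

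**What to change.** State one participant flow in Section 9.2 and carry the same numbers into Sections 1.1, 2.1, 4.2 and 6.3: women enrolled at week 0, assumed loss from week 0 to week 8, number randomised per arm, and expected completers. The sponsor should choose the version that matches its intention.

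- **If Section 9.2 governs:** say that 250 is the week 0 enrolment into the baseline phase, and give the assumed loss before randomisation. Randomisation closes at 138 (69 per arm, replacing 60 in Sections 4.2 and 6.3), with about 117 expected to complete and about 89% completer-based power. Relabel 138 as the number randomised.
- **If 120 is the number randomised:** keep 60 per arm, and restate Section 9.2 with 102 expected completers and about 84% power. Explain the 250 in the same way.
- **If all 250 are to be randomised:** restate Sections 4.2, 6.3 and 9.2 for that number.

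The cost is wording in five sections. No additional enrolment is proposed beyond what the protocol already prints, and no new procedures are needed.

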2.2 BACKGROUND

Clinical, basic, and epidemiologic research indicates that reproductive events provide an endocrine context of vulnerability for the emergence of mood and anxiety disorders and impairment in women¹. Though the causes of affective disorders tied to reproductive events are unknown, studies in menstrual mood disorders and postpartum depression suggest that a vulnerability to normal changes in ovarian steroid hormones is etiologic^{2,3}. The menopause transition ('perimenopause') is a reproductive stage associated with pronounced hormone variability and risk for psychiatric illness. The menopause transition (MT) is an ideal model for studying the etiologic role of ovarian hormone changes in affective illness.

During the MT (average duration = 5 years), the risk of major depressive disorder (MDD) increases two to three-fold⁴, in addition to the two to four-fold increase in risk of clinically significant depressive symptoms, affecting 26-33% of women in the MT⁵⁻⁸. A parallel increase in suicide ideation and attempts emerges in perimenopausal compared with pre- or postmenopausal women or age-matched men. While the causes of perimenopausal affective disorders are unknown, stressful life events are a strong predictor of the development of depression in the MT⁴⁻⁶.

The Phenotype of Perimenopausal Depression: Women in the MT with impairing mental health symptoms typically present with an anxious and anhedonic phenotype⁹⁻¹¹. Common to all anxiety

disorders is an exaggerated neurobiological sensitivity to threat, indexed by cognitive biases to regard ambiguous stimuli as threatening^{12,13}. The brain regions involved in processing threat information (e.g., hippocampus) activate stress-responsive systems, including the hypothalamic-pituitary-adrenal (HPA) axis. Perceived threat is a feature of stress that elicits cortisol increases¹⁴. Anhedonia (loss of pleasure or interest) has emerged as an endophenotype in depressive disorders¹⁵. Patients with anhedonia exhibit diminished sensitivity and attentional bias towards positively valanced stimuli and reduced behavioral and neurobiological responsiveness to reward cues¹⁵. Anhedonia can be defined as reduced motivation to approach rewards (reward “wanting”).

This research will employ a more fine-grained approach to defining impairment in perimenopausal women by focusing on anxiety and anhedonia symptoms. This will allow for more precise integration of a particular psychopathology with underlying biological mechanisms (E2 regulation of HPA axis reactivity) and fundamental constructs (threat responsivity and approach motivation), and therefore advance our knowledge of the causes of the clinical impairment experienced by 25% of women in the MT.

Endocrinology of the Menopause Transition: While there are individual differences in the hormonal trajectory during the MT^{16,17}, most women experience the following changes beginning in the early and progressing to the late MT^{18,19}. First, cycle length becomes increasingly variable, with long cycles becoming more common as the transition progresses. While short cycles are due to early follicular recruitment by intermittently high FSH, long cycles can be due to anovulation or a delayed ovarian response to FSH stimulation, resulting in an extended (low-E2) early follicular phase. Second, luteal progesterone (P4) also declines, resulting from declining dominant follicle quality. Third, appearing in the early and continuing into the late MT are cycles in which E2 levels are elevated compared to premenopausal levels, due to high FSH and ovarian hyperstimulation²⁰. The late MT is marked by more anovulatory cycles, characterized by low P4 and erratic E2. In sum, most women in the MT are exposed to erratic hormonal flux. Anovulatory cycles results in fewer increases in P4, but variable FSH causes periods of both hypo- and hyper-estrogenism²¹.

The Hormone Milieu and Affective Symptoms in the Menopause Transition: While women in the MT are exposed to periods of relative hyper-estrogenism, mean levels of E2 are lower than in premenopausal women^{22,23}, especially in late MT. Whether the clinical symptomatology experienced during the MT is consequent to E2 deprivation or E2 variability has not been empirically tested. Estradiol: 1) “beneficially” modulates systems implicated in depressive illness (e.g., neurotransmitters, neuroplasticity)²⁴⁻²⁷; 2) displays anti-depressant effects in animals²⁸⁻³¹; 3) regulates brain circuits important for emotional processing³² and fear conditioning³³ and protects against fear and anxiety³⁴. While the planned research will test whether alterations in the neurobiologically based constructs of threat reactivity and approach motivation underlying anxiety and anhedonia is best explained by E2 variability or E2 levels, most evidence supports the variability hypothesis³⁵⁻⁴⁵. Schmidt et al.,⁴⁶ placed euthymic perimenopausal women (CES-D = 3) on three weeks of transdermal E2 (100 ug/day) then blindly and abruptly withdrew half of the women. Those with a history of perimenopausal depression (PMD) had an increase in depressive symptoms (CESD = 12) within 1-3 weeks, an effect not seen in unaffected controls or in those maintained on E2. The specific symptoms that increased with abrupt E2 withdrawal were only: anxiety, excessive worry, anhedonia, motivation, and social avoidance – supporting an etiologic role for E2 in the clinical anxiety and anhedonia experienced in the MT. However, that study did not measure E2, limiting conclusions about the mechanism underlying emergence of symptoms (i.e., withdrawal from E2 stabilization or induction of E2 deprivation). Our prior research strongly implicates E2 variability, not levels⁴⁷.

E2 regulation of the HPA axis as a Candidate Mechanism in the Psychopathology of the MT: Impairment in HPA axis regulation is implicated in human affective illness⁴⁸. Gonadal steroid hormones play a vital role in modulating HPA axis function. Estrogens stimulate the HPA-axis through an interaction of estrogen receptors (ERs) in the promoter region of the human CRH gene ⁴⁹. ERs are expressed throughout the brain ⁵⁰, including the paraventricular nucleus of the hypothalamus. The genomic action of E2 is mediated by ER α and ER β . E2 also has rapid cellular effects by inducing changes in second messenger pathways and intracellular Ca²⁺ ^{51,52}. Although ERs are abundant in regions involved in affect regulation^{53, 54,55}, E2 regulatory control of the HPA axis may be most relevant to understanding anxiety and anhedonia in the MT, particularly in the context of stressful life events.

In rodents, ovariectomy reduces stress-induced corticosterone (CORT) and ACTH secretion, an effect reversed by systemic E2 treatment ^{56, 57,58}. Acute stress increases production of E2 in the PVN⁵⁹ and its presence is associated with enhanced responsiveness of the HPA axis to stress, mediated by E2-induced impairment in glucocorticoid negative feedback⁵⁷. The effect of E2 depends on the ER signaling pathways⁶⁰ since stimulation of ER α and ER β , exerts opposite effects on the CORT and ACTH stress response ^{56,59-61}. Consequently, alternations between hyper- and hypo-estrogenism, characteristic of the MT, could exert a destabilizing effect on the regulatory control of the HPA axis. Testing HPA stress reactivity as a mediator in the relationship of E2 variability (or levels) to threat responsivity and approach motivation, and clinical symptoms, in perimenopausal women represents a novel contribution of this research.

The significance and impact of the proposed research is in delineating the role of E2 variability versus E2 levels in the clinical symptoms seen in a substantial proportion of women in the MT and testing a candidate physiologic mediating mechanism (HPA axis) of E2. This research will advance a diathesis-stress model of affective state change involving E2 (variability or levels) as the diathesis for HPA axis dysregulation and affective symptoms, in the context of severe life stress.

